8.1. Analysis set

All analyses are performed for the full analysis set⁷.

8.2. Variables

Data file, identifier patient_display_id_full	Descriptive	Variable name	Variable label	Variable level	Nominal values
implantation_general_data	Yes	imp_group	Patient Group	nominal	Device of the Ilivia family (group A) Plexa right ventricular lead (group B) Both Ilivia and Plexa (group AB)

Baseline / Demographics

Data file, identifier patient_display_id_full	Descriptive	Variable name	Variable label	Variable level	Nominal values
baseline	Yes	bas_age	Age	scale	n.a.
baseline	Yes	bas_weight	Weight [kg]	scale	n.a.
baseline	Yes	bas_height	Height [cm]	scale	n.a.
baseline	Yes	bas_bmi	BMI [kg/m2]	scale	n.a.
baseline	Yes	bas_sex	Gender	nominal	Male Female

The total study duration will be calculated as the total sum of all patients' time between informed consent and termination. If a patient's study participation is terminated earlier for one of the study arms A or B, the later termination date will be used for this patient.

This total study duration will be used to calculate the mortality in deaths per 100 patient-years.

Additionally:

- Number of all patients, that signed the informed consent
- Number of patients in the full analysis set, in the Ilivia analysis set (A) and in the Plexa analysis set (B), and number of patients in both the Ilivia and the Plexa analysis set (AB)
- Number of regular terminations (altogether and per group)
- Number of patients with early study termination (split by reason for early termination, altogether and per group)

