8 DESIGN OF THE CLINICAL INVESTIGATION

8.1 General considerations

The study is designed as a multicenter, international, non-randomized, open-label and prospective study including two subgroups: **group A** with the Ilivia ICD family and **group B** with the Plexa right ventricular ICD lead.

Patients can be enrolled into both groups, if they receive both study devices, see below for details.

Group A
Ilivia ICD family

Enrollment:

In group A, a total of 105 patients will be enrolled. With an expected drop-out rate of 10% a minimum number of 94 patients will be included in the analysis set. In total, 26 patients should receive a single chamber ICD, 26 patients a dual chamber ICD and 53 patients a triple chamber ICD (CRT-D).

Group B
Plexa ICD lead

Enrollment:

In group B, a total number of 185 patients will be enrolled. With an expected drop-out rate of 10% a minimum number of 166 patients will be included in the analysis set.

Tab. 4: Required visit windows (1 month is defined as 30 days)

	Window	Days post-implant
Pre-hospital discharge or wound check	+ 10 days	0 to 10
3 months post-implant	± 30 days	61 to 121
6 months post-implant	± 30 days	151 to 211

[figure not shown]

Fig. 4: Follow-up scheme of group A (Ilivia ICD family) and group B (Plexa ICD lead)

Patients in group A and/or group B will be followed for duration of 6 months in the BIO|MASTER.Ilivia Family / Plexa study. During this time 5 visits are planned per patient: Enrollment, Implantation, Pre-hospital discharge, 3-month follow-up and 6-month follow-up (Fig. 4). The implantation shall be performed within 30 days after enrollment of the patient. The other windows associated with each visit are provided above in Table 4. This schedule should be followed as closely as possible. If circumstances prevent the presence of the patient at the follow-up visit, the reason for the missed follow-up has to be indicated on the eCRF. In addition, interim evaluations for device related revisions will be performed.

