9.2 Enrollment

Prior to enrollment into the clinical investigation, all patients will be evaluated by their physician for fulfilling the inclusion criteria. For valid enrollment the informed consent form has to be signed and dated by the patient and also signed and dated by the investigator. The informed consent process has to be documented in the patient record. In case date of enrollment is identical with date of implantation, the exact time of informed consent shall be entered in the patient record to document that informed consent has been obtained prior to any study-specific procedure.

The signed informed consent will be verified by the monitor. The date of enrollment is defined by the patients` signature date of the informed consent. The investigator has to check whether all inclusion criteria are met and the absence of all exclusion criteria is confirmed.

On the Enrollment eCRF the following data have to be recorded:

- Information on informed consent process
- Check of inclusion and exclusion criteria

On the Baseline eCRF the following data have to be recorded:

- Patient's demographics
- Indication for ICD or CRT-D therapy
- Comorbidities
- Current cardiovascular medication
- ECG diagnostics (if available within 3 months prior to implantation)
- For CRT-D patients: LVEF and NYHA class evaluated within 3 months prior to implantation

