
Frequency not assessable on the basis of the available data
		
diaphragmatic stimulation³², discomfort, erosion, exit block³², failure to insulate set screw³², hemoptysis³², injury to vagus nerve³², lead malpositioning³², lead micro-dislodgement³², local tissue reaction³⁰, muscle stimulation³⁰, nerve stimulation (general)³⁰, myocardial lesion³⁰, pocket seroma³², subclavian artery puncture³², higher x-ray load due to extended fluoroscopy times³⁴, failing of shock test⁴⁰, injury due to implantation accessories^{42,44}

--	--	--

Tab. 8b: Expected post-operative events based on literature research

Frequency	Percentage (%)	Risk
	9.7 ²⁰ - 37 ²³	Lead failure ^{20,22,23}

Very frequent >1 out of 10 patients
	2.9 ⁷ - 25.4 ²⁴	Inappropriate shocks ^{7,24,25,54}
	Up to 13 ²⁹	Device explantation (manufacturers` advisory: 4% ²⁹ , electronic failure: 2% ²⁹ , housing defects: 1% ²⁹)
	0.3 ¹ - 13.6 ⁴	Phrenic nerve stimulation
	12 ^{6,21}	Lead dysfunction
	1.2 ¹⁹ - 10.6 ²	Lead dislodgement

Frequent 1 to 10 patients out of 100
	1.7 ² - 9.5 ²	Formation of clinical significant hematomas
	7.6 ¹⁵ - 9.5 ¹	Hematoma ^{1,3,15,16,17}
	7 ⁴⁶	Subclavian vein occlusion ≥ 75%
	0.1 ⁵ - 7 ¹	Infections ^{1,5,14} (CRT-D related: 1.9 ^{1,4,13} - 1.9% ^{1,4} ; in-hospital infections: 0.7% ¹² ; infections after replacement: 1.9% ¹³)
	0.1 - 4.2 ⁶⁰	Lead fracture
	1.6 ⁷ - 3.9 ⁴	Elevated pacing threshold/ loss of capture/ failure to capture
	2.4 ³⁰	Aggregate perforation
	3.4 ³⁰	Pocket erosion
	0 ² - 1.5 ⁷	Mortality within 30 days after implant (0.4% related to implant procedure ⁷)
	1.5 ³⁰	Premature depletion of battery
	1.4 ⁷	Diaphragmatic muscular stimulation
	0.3 ² - 1.3 ⁵	Lead perforation
	1.3 ¹	Pericarditis requiring anti-inflammatory agents
	0.05 ⁷ - 1,2 ^{12,57,61}	Pneumothorax
	0.9 ¹	High LV threshold
0.7 ⁵	Oversensing	
0.6 ⁷	Discomfort	
0.6 ⁷	Pain at device pocket	

FOR-137-014-C / SOP-137-020.020 / CRQ-14-01202

	0.6 ¹	Pericardial effusion requiring intervention
	0.6 ⁷	Seroma
	0.6 ⁷	Shoulder pain
	0.5 ⁴	Lead conductor fracture
	0.5 ³⁰	M. pectoralis tremor
	0.3 ⁵ – 0.5 ¹⁸	Post-operative perforation
	0.7 ⁵⁴	Thrombosis of brachial, subclavian or jugular veins
	0.3 ¹²	Acute renal failure requiring hemodialysis
	0.3 ¹	Ipsilateral venous thrombosis
	0.3 ⁷	System- or lead-related arrhythmia
	0.2 ⁴	Elevated lead impedance
	0.2 ⁶³	Site pain
	0.2 ⁵⁴	Thrombosis of deep femoral vein
Rare 1 to 10 patients out of 10.000	0.09 ³⁵	Fluid accumulation due to heart perforation

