7.1. Full Analysis Set

Data file, identifier patient_display_id_full	Variable name	Variable label	Variable level	Nominal values
enrollment	DMSUBIC	Patient has provided written informed consent	nominal	Yes /No
data_SAR	analysis_set_full_SAR ⁴	Full analysis set	nominal	Yes / No

² IF end_group_term = Yes, group A terminated
THEN enddate_Ilivia_SAR = end_group_term_date
ELSE enddate_Ilivia_SAR = end_visdate

³ IF end_group_term = Yes, group B terminated
THEN enddate_Plexa_SAR = end_group_term_date
ELSE enddate_Plexa_SAR = end_visdate

⁴ IF DMSUBIC = Yes
THEN analysis_set_full_SAR = Yes
ELSE analysis_set_full_SAR = No

All rights pertaining to this document are exclusively held by BIOTRONIK SE & Co. KG. Any non-authorized copying, reproduction or distribution is not permitted. Confidentiality: This document and/or its contents are only for internal use.

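### The one planned mortality rate runs from consent and pools all patients, so it cannot show early post-implant mortality or give a rate per device set

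*SAP*

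**What the plan says.** SAP 8.2 defines the person-time: "The total study duration will be calculated as the total sum of all patients' time between informed consent and termination". It then states its use: "This total study duration will be used to calculate the mortality in deaths per 100 patient-years". For a patient who leaves one group before the other, the later termination date applies.

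The population comes from SAP 8.1: "All analyses are performed for the full analysis set". SAP 7.1 gives that set a single condition, written consent ("IF DMSUBIC = Yes"). Neither implantation nor contact with a device is required.

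On timing, protocol (CIP) 8.1 says: "The implantation shall be performed within 30 days after enrollment of the patient". Same-day consent and implantation is foreseen in CIP 9.2: "In case date of enrollment is identical with date of implantation, the exact time of informed consent shall be entered in the patient record". Planned follow-up is six months (CIP 8.1: "Patients in group A and/or group B will be followed for duration of 6 months").

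CIP 18.7 has two mortality rows among its anticipated events. Tab. 8a gives 0.5 to 0.7% peri-operatively. Tab. 8b has a row for "Mortality within 30 days after implant" at 0 to 1.5%, of which 0.4% relates to the procedure.

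The SAP defines no other mortality rate, no 30-day figure and no time-to-death analysis.

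**The concern.** The study exists to find residual risks of two implanted devices, and death is the gravest of them. Three features of the planned rate limit what it can say.

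- **Clock.** Time before implantation, when no study device is in place, counts as time at risk.
- **Timing.** One average over about six months cannot separate deaths soon after surgery from deaths late in follow-up. The CIP expresses its anticipated mortality for the early period.
- **Pooling.** There is one figure for the whole study, so neither device set has a mortality rate.

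The SAP treats serious adverse device effects differently. Sections 16 and 23 count from the implantation date (imp_visdate), separately for the Ilivia and Plexa sets, and add a Kaplan-Meier estimate at 91 days. Death gets a different clock, population and method, and no reason is given.

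**Working it through.** The documents state no expected mortality, patient-years or precision for mortality, so there is no planned figure to reproduce. The check asks how far the definition can move or mask the result.

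**Inputs.** Consent to implant takes 0 to 30 days (CIP 8.1, 9.2); the typical delay is not given, so values in between are assumptions. Follow-up is 180 days, with a visit window of 151 to 211 (CIP Tab. 4). There are up to 290 patients (CIP synopsis), or 185 if every group A patient is also in group B. For scale, the Lumax 740 study had 3 deaths in 183 patients over 6 months (CIP 5.2.1). A year is 365.25 days.

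**1. Pre-implant share of person-time.** For an implanted patient who completes follow-up, with d days from consent to implant, the share is d/(d + 180).

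| d (days) | Share |
|---|---|
| 0 | 0% |
| 3 | 3/183 = 1.6% |
| 7 | 7/187 = 3.7% |
| 14 | 14/194 = 7.2% |
| 30 | 30/210 = 14.3% |

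At d = 30, the ends of the visit window give 30/181 = 16.6% and 30/241 = 12.4%.

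**2. Effect on a rate.** Rate = 100 × deaths / patient-years. With the Lumax counts:

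- From implant: 300 / (183 × 180/365.25) = 300/90.2 = 3.33.
- With 7 pre-implant days each: 300 / (183 × 187/365.25) = 300/93.7 = 3.20.
- With 30 days each: 300 / (183 × 210/365.25) = 300/105.2 = 2.85.

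This assumes no pre-implant deaths. In general, the planned rate is a person-time-weighted average of the pre-implant and post-implant rates. It understates the latter only if the former is lower.

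**3. Loss of timing.** Take 4 deaths in 290 patients, no pre-implant time, and the other 286 followed for 180 days.

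- All on day 15: (286 × 180 + 4 × 15)/365.25 = 141.1 patient-years; 400/141.1 = **2.83**. The 30-day mortality is 4/290 = 1.38%.
- All on day 150: (286 × 180 + 4 × 150)/365.25 = 142.6 patient-years; 400/142.6 = **2.81**. The 30-day mortality is 0%.

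Seen the other way, 1.5% mortality by day 30 is 1.5/(30/365.25) = 18.3 per 100 patient-years inside that window. With no later deaths it averages to 1.5/(180/365.25) = 3.04 over 180 days from implant, or 2.61 over 210 days from consent.

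**4. What a 30-day proportion would deliver.** At 1.5%, expected deaths are 185 × 0.015 = 2.8 to 290 × 0.015 = 4.4; at 0.4%, 0.7 to 1.2. The exact (Clopper-Pearson) 95% interval for 4/290 is 0.4% to 3.5%. With no deaths, the upper limit is 1 − 0.025^(1/N): 1.3% for 290, 2.0% for 185 and 3.5% for 105.

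**The case against.** The other side has a good deal right.

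- **The dilution is small and rests on an assumed delay.** It is zero with same-day consent and reaches 14.3% only if every patient waits the full 30 days. With 3 deaths in 183 × 0.5 = 91.5 patient-years, the exact Poisson 95% interval is about 0.7 to 9.6 per 100, so the dilution is far inside sampling error. Patients with a failed implantation add only their time to the last attempt (CIP 8.8.5). This stands.
- **A reader might infer that the rate must be biased low.** The documents do not support that. Event collection starts at consent, so pre-implant deaths enter the numerator too.
- **A reader might infer that the rate assumes a constant hazard.** It does not: deaths over person-time is an average rate.
- **A reader might infer that it cannot be compared with the Lumax 740 result.** It can, since that result converts to the same unit. Only the 30-day comparison is lost.
- **A reader might take the Tab. 8a and 8b rows as benchmarks.** They are literature figures for anticipated events, two rows among many.
- **Other outputs may reveal deaths.** SAP 8.2 counts early terminations by reason and group, and SAP 7.2 lists early drop-outs with patient, group and reason. This stands only in part. Neither output carries dates, the list of reasons is abridged, and the SAP has no chapter tabulating adverse events. A raw death count is likely; its timing is not planned.
- **Per-set figures would share patients and deaths,** because the groups overlap by design. This stands, and calls for a note beside the table.

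**Conclusion.** The point holds as a gap in descriptive safety reporting. The only planned mortality rate starts at consent, pools all consenting patients and cannot distinguish early from late deaths: 2.83 against 2.81 per 100 patient-years in the example, for 30-day mortality of 1.38% against 0%. The timing loss is the main weakness. The pre-implant share is secondary, and its size depends on a delay the documents do not report. The number of distinct patients (185 to 290) is likewise a range.

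Mortality is neither a primary nor a secondary endpoint, so it would be wrong to infer any threat to the primary tests, significance level, sample size or pass/fail rule. The change is still worth making: the SAP already applies the better clock and the per-set analysis to its device-effect endpoints.

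**What to change.** In SAP 8.2:

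1. Start the patient-year clock at imp_visdate, among patients with an implantation attempt.
2. List deaths between consent and implant separately.
3. Add deaths within 30 days of implant as n/N with an exact 95% interval, overall and for the Ilivia and Plexa analysis sets, noting that the sets overlap. State beside it how many patients left the study alive before day 30.
4. Optionally, add a Kaplan-Meier estimate of all-cause mortality at 6 months.

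No new data are needed. The SAP holds the implantation date (6.2) and group-specific termination dates (6.3), death sets the termination date (CIP 8.8.5), and date and time of death are recorded (CIP 18.4.1). The cost is a little more analysis work, a stated rate that may be slightly higher, and wide per-set intervals.

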8.3. Treatment of Missing and Spurious Data

See general definitions in chapter 5.4.

8.4. Exclusion of Particular Information

See general definitions in chapter 5.5.

8.5. Descriptive Analyses

See general definitions in chapter 5.1.

⁷ analysis_set_full_SAR = Yes

8.6. Hypotheses & Statistical Tests

There are no pre-defined statistical hypotheses.

9. Baseline Data: Ilvia

9.1. Analysis set

All analyses are performed for the Ilvia analysis set⁸.

9.2. Variables

Baseline / Demographics

Data file, identifier patient_display_id_full	Descriptive	Variable name	Variable label	Variable level	Nominal values
baseline	Yes	bas_age	Age	scale	n.a.
baseline	Yes	bas_weight	Weight [kg]	scale	n.a.
baseline	Yes	bas_height	Height [cm]	scale	n.a.
baseline	Yes	bas_bmi	BMI [kg/m2]	scale	n.a.
baseline	Yes	bas_sex	Gender	scale	Male / Female

Baseline / Indications

Data file, identifier patient_display_id_full	Descriptive	Variable name	Variable label	Variable level	Nominal values
baseline	Yes	bas_heart_disease	Underlying heart disease	nominal	Ischemic Non-ischemic
baseline	Yes	bas_indication	ICD indication	nominal	Primary prevention Secondary prevention
baseline	Yes	bas_pacing_dependent	Pacemaker-dependency	nominal	Yes / No
baseline	Yes	bas_hf	heart failure	nominal	Yes / No
baseline	Yes	bas_lbbb	Left BBB	nominal	Yes / No
baseline	Yes	bas_rbbb	Right BBB	nominal	Yes / No
baseline	Yes	bas_nyha	heart failure status	nominal ⁹	NYHA I NYHA II NYHA III NYHA IV
baseline	Yes	bas_atrial_rhythm	Current Atrial rhythm	nominal	[...] sinus rhythm Sinus bradycardia Sinus Tachycardia Atrial Fibrillation Atrial Flutter Other SVT
baseline	Yes	bas_avblock	AV block	nominal	None I° II° III°
baseline	Yes	bas_af_type	History of atrial fibrillation (according to ESC guidelines)	nominal	Paroxysmal (usually ≤ 48h) Persistent (> 7 days [...]) Long-standing persistent [...] Permanent (accepted)

⁸ analysis_set_Ilvia_SAR = Yes

⁹ No conversion to ordinal data planned e.g. to calculate Median and inter-quartile range

					None
baseline	Yes	bas_qrs	QRS Duration [ms]	scale	n.a.
baseline	No	bas_rr_interval	Mean RR-interval	scale	n.a.
baseline	No	bas_heart_rate	mean heart rate	scale	n.a.
baseline	Yes	bas_heart_rate_SAR ¹⁰	mean heart rate [bpm]	scale	n.a.
baseline	Yes	bas_lvef	LVEF [%]	scale	n.a.

Baseline / Diseases

Data file, identifier patient_display_id_full	Descriptive	Variable name	Variable label	Variable level	Nominal values
baseline	Yes	bas_comorb_01	Hypertension [...]	nominal	Yes /No
baseline	Yes	bas_comorb_02	History of TIA / Stroke	nominal	Yes /No
baseline	Yes	bas_comorb_03	Peripheral vascular disease	nominal	Yes /No
baseline	Yes	bas_comorb_04	Asthma or other [...]	nominal	Yes /No
baseline	Yes	bas_comorb_05	[...] (COPD)	nominal	Yes /No
baseline	Yes	bas_comorb_06	Renal dysfunction	nominal	Yes /No
baseline	Yes	bas_comorb_07	Sleep apnoea	nominal	Yes /No
baseline	Yes	bas_comorb_08	Liver disease	nominal	Yes /No
baseline	Yes	bas_comorb_09	Diabetes mellitus	nominal	Yes /No
baseline	Yes	bas_comorb_10	Anemia	nominal	Yes /No
baseline	Yes	bas_comorb_11	Cancer	nominal	Yes /No

Baseline / Medication

Baseline medication is reported only, whereby "Other" medications, and medication names, are not reported.

Data file including rows for each medication per patient per date	Descriptive	Variable name	Variable label	Variable level	Nominal values
cm_embedded_log	No	CMBLFL	Baseline medication	nominal	Yes / No
cm_embedded_log	No	CMCLAS	Medication class		ACE inhibitors Angiotensin receptor blocker Aldosterone blocker Betablocker (excluding sotalol) Calcium channel blocker Digoxin Statins Diuretics Anticoagulation Antiplatelets Antiarrhythmics Other

¹⁰ IF bas_heart_rate ≠ missing THEN bas_heart_rate_SAR = bas_heart_rate
ELSE IF bas_rr_interval ≠ missing THEN bas_heart_rate_SAR = 60000 / bas_rr_interval

Data file, identifier patient_display_id_full	Descriptive	Variable name	Variable label	Variable level	Nominal values
data_SAR	Yes	med01_SAR ¹¹	ACE inhibitors	nominal	Yes /No
data_SAR	Yes	med02_SAR ¹²	Angiotensin receptor blocker	nominal	Yes /No
data_SAR	Yes	med03_SAR ¹³	Aldosterone blocker	nominal	Yes /No
data_SAR	Yes	med04_SAR ¹⁴	Betablocker (excluding sotalol)	nominal	Yes /No
data_SAR	Yes	med05_SAR ¹⁵	Calcium channel blocker	nominal	Yes /No
data_SAR	Yes	med06_SAR ¹⁶	Digoxin	nominal	Yes /No
data_SAR	Yes	med07_SAR ¹⁷	Statins	nominal	Yes /No
data_SAR	Yes	med08_SAR ¹⁸	Diuretics	nominal	Yes /No
data_SAR	Yes	med09_SAR ¹⁹	Anticoagulation	nominal	Yes /No
data_SAR	Yes	med10_SAR ²⁰	Antiplatelets	nominal	Yes /No
data_SAR	Yes	med11_SAR ²¹	Antiarrhythmics	nominal	Yes /No
data_SAR	Yes	med01_02_SAR ²²	ACE inhibitors OR Angiotensin receptor blocker	nominal	Yes /No

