8.4.1 Further data of interest in group A (Ilivia ICD family)

- MPP settings

The MPP settings used by the physicians will be collected for all CRT-D patients programmed to MPP "on". This includes the programmed vectors, the pacing threshold, the programmed pacing amplitudes, the LV sensing polarity, the sensing amplitude, the LV-LV and RV-LV delay as well as any change of setting during the course of the study.

- Handling of MPP programming (interface programmer)

The physician is asked to evaluate the handling of the MPP programming in an eCRF "MPP handling".

- SADE related to MPP during 6 months

SADEs which are possibly or securely related to MPP will be listed in a descriptive manner.

- Rate of responders/ non-responders to CRT therapy

These data will be collected from all patients implanted with a CRT-D device of the Ilivia family. The physician should evaluate at the 6-month follow-up if the respective patient is a responder or a non-responder to CRT-D therapy. Patients who did not tolerate MPP and had to be reprogrammed to MPP "off" during the course of the study contribute to the MPP "off" group.

- NYHA class, change of NYHA class in CRT-Ds

The NYHA class will be collected at baseline from all patients and at 6-month follow-up for CRT-D patients only. The mean change of NYHA class in CRT-D patients between enrollment and 6-month follow-up will be evaluated.

- Percentage of DX devices among devices, DX in CRT, atrial sensing amplitude in DX devices

Data of DX devices will be collected, including the percentage of used DX devices in ICD and CRT-D therapy. Furthermore the atrial sensing amplitude of DX devices as well as CRT statistics will be collected and the mean values evaluated at 3- and 6-month follow-up.

- Ventricular therapy episodes

Ventricular therapy and therapy attempt episodes will be collected and documented in a tachyarrhythmia episode eCRF, IEGMs of the episodes will be collected.

- Programming of Early ATP one-shot

The number of programming of Early ATP one-shot will be documented for all patients with programming of ATP one-shot in the VF zone. Number of occurred Early ATP one-shot will be collected based on the documented ventricular tachycardia IEGM episodes.

- Lead measurements (sensing amplitude, pacing threshold, pacing impedance, shock impedance) via pacing sensing analyzer (PSA) during implantation

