 5. Evaluate ventricular ICD therapy/therapy attempt episodes: open and store IEGMs of all episodes; all VF and VT episodes according to device detection. Evaluate each episode on the Tachyarrhythmia episode form. Furthermore, evaluate the last 3 episodes with fast ventricular rhythm (SVT, nsVT) prior to the follow-up, if available (**group A**).
 6. Open and store IEGMs of all event-triggered episodes: therapies, non-sustained VTs, fast intervals and atrial episodes (**group A and B**).
 7. Document MRI examinations since last follow-up in eCRF "MRI AutoDetect form", if applicable (**group A**).
 8. Report all adverse events. In case of a serious adverse event, or adverse device effect (ADE), please provide the information immediately to BIOTRONIK, and inform the ethical committee, if required. If the ICD or lead is exchanged or repositioned the follow-up schedule is adapted as described in section 9.8 "Interim Intervention". Report adverse events within the indicated timelines (see 18.9).
 9. Complete the electronic Case Report Form (eCRF) immediately.

9.6 6-month follow-up

Patients have to return for a final follow-up visit, six months (± 30 days) after the implantation procedure. The study procedures performed at this visit are identical with the procedures for the 3-month follow-up with exception of the evaluation of sensing and pacing performance.

In addition for patients in **group A** the following assessments have to be performed:

- Determine NYHA class of the patient (CRT-D only)
- Define if patient is considered a responder or non-responder to CRT-D therapy (CRT-D only)

After this follow-up procedure the patients will officially terminate the BIO|MASTER.Ilivia Family / Plexa Study.

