5.1. Descriptive analyses

CIP chapter 11.1 Statistical design, methods and analytical procedures

For continuous variables descriptive statistics (mean, standard deviation, minimum, 1. quartile, median, 3. quartile and maximum) will be calculated. For nominal variables absolute numbers and relative frequencies based on the non-missing data will be determined. Ordinal data are described by the 1. quartile, median, and 3. quartile as well as the absolute numbers and relative frequencies based on the non-missing data of each category

Ordinal data are described by the absolute numbers and relative frequencies based on the non-missing data of each category and by the 1. quartile, median and 3. quartile, when appropriate.

For illustration, see the following standard tables based on dummy data.

Nominal - dichotomous

Variable label	Category	Missing data	Non-missing data	Absolute frequency	Relative frequency [%]
Sex	Female	1	9	5	55.6
History of AF	Yes	2	8	4	50.0

Nominal – more than two categories

NYHA class, all patients	Absolute frequency	Relative frequency [%]
NYHA I	5	62.5
NYHA II	1	12.5
NYHA III	1	12.5
NYHA IV	1	12.5
Sum	8	100.0

NYHA class, all patients; N total =10; N missing = 2

Scale / metric

Variable	N non-missing	N missing	Mean	SD	Min	Lower quartile	Median	Upper quartile	Max
Age [years]	7	3	51.7	15.0	25.0	40.0	57.0	60.0	70.0
Height [cm]	8	2	177.3	14.4	150.0	170.0	179.0	187.5	195.0
Weight [kg]	7	3	77.1	14.5	55.0	69.0	77.0	90.0	99.0

Ordinal

Variable	N non-missing	N missing	Min	Lower quartile	Median	Upper quartile	Max
NYHA class	8	2	1.0	1.0	1.0	2.5	4.0
Patient self assessment	8	2	1.0	1.0	1.0	2.0	3.0

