14.1. Analysis set

All analyses are performed for the Ilivia analysis set⁶⁸.

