14.2. Variables

6mFU / General data

Data file, identifier patient_display_id_full	Descriptive	Variable name	Variable label, NEW prefix added to all labels "6mFU data: "	Variable level	Nominal values
fu_6_month_general_data	No	fu6_visdate	Date of 6-month follow-up	date	n.a.
fu_6_month_general_data	Yes	fu6_not_done	visit not performed	nominal	True / False
fu_6_month_general_data	Yes	fu6_interim	Did another follow-up occur since 3-month Follow-up	nominal	Yes / No
fu_6_month_general_data	Yes	fu6_interim_reason	NEW: Reason for another FU	nominal	Home Monitoring alert Medical symptoms Other

6mFU / General Data / Heart Failure

Data file, identifier patient_display_id_full	Descriptive	Variable name	Variable label, NEW prefix added to all labels "6mFU data: "	Variable level	Nominal values
fu_6_month_general_data	No	fu6_hf	Heart failure	nominal	Yes / No
fu_6_month_general_data	Yes	fu6_nyha	Heart failure status	nominal	NYHA I NYHA II NYHA III NYHA IV
fu_6_month_general_data	Yes	fu6_responder	Responder to CRT-D therapy	nominal	Yes / No

⁶⁸ analysis_set_Ilivia_SAR = Yes

The following variables are analyzed as defined for the Ilivia analysis set, as described in chapter 13.2.

6mFU Device Data / RA

6mFU Device Data / RA / Not-measured

6mFU Device Data / RV

6mFU Device Data / RV / Not-measured

6mFU Device Data / LV / Programmed Sensing Vector

6mFU Device Data / LV / Programmed Sensing Vector / Not-measured

6mFU Device Data / LV / Programmed Pacing Vectors

6mFU Device Data / LV / Programmed Pacing Vectors / Not-measured

6mFU Device Data / LV / Vector Change

6mFU Device Data / LV / Programmed Delay

6mFU Device Data / CRT / Atrial burden

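### The protocol promises the mean NYHA change in CRT-D patients, but the SAP specifies only two unpaired frequency tables that cover different patients

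*SAP*

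**What the plan says.** **Protocol.** Section 8.4.1, on further data of interest in group A, sets out who is measured and when: "The NYHA class will be collected at baseline from all patients and at 6-month follow-up for CRT-D patients only". It then names the analysis: "The mean change of NYHA class in CRT-D patients between enrollment and 6-month follow-up will be evaluated". Table 7 and section 9.6 confirm that the 6-month assessment is for CRT-D patients only. Table 7 marks baseline NYHA as collected if available. Section 9.2 lists baseline NYHA under an entry for CRT-D patients, which can be read as restricting it to them.

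**SAP.** Chapter 1 says that the document gives instructions for all mandatory analyses.
- Baseline: SAP 9.1 states "All analyses are performed for the Ilvia analysis set". SAP 9.2 lists bas_nyha as nominal, and footnote 9 adds "No conversion to ordinal data planned e.g. to calculate Median and inter-quartile range".
- Six months: SAP 14.1 states "All analyses are performed for the Ilivia analysis set". SAP 14.2 lists fu6_nyha, labelled "Heart failure status", as nominal with categories NYHA I to IV.
- Summary rule, SAP 5.1: "For nominal variables absolute numbers and relative frequencies based on the non-missing data will be determined".
- SAP 5.6 plans no subgroups beyond the split into Ilivia and Plexa.

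Neither chapter 9 nor chapter 14 defines a NYHA change, a paired set or a shift table.

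**The concern.** A change is a within-patient quantity: it needs both values from the same patients. The protocol specifies it that way, giving the population, the two time points and the statistic. The SAP reduces it to two marginal frequency tables whose denominators differ by design. The baseline table includes single- and dual-chamber ICD patients, who have no 6-month value.

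Two things are at stake. A result promised in the protocol would be missing from the report without anyone having decided to drop it. A reader who looks for it would also be likely to set the two tables side by side and take the difference as the change, although it mixes the true change with the difference in case mix between device types and with loss between visits.

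**Working it through.** **Step 1: what the SAP outputs.** Under SAP 5.1 a nominal variable yields counts and percentages of the non-missing values. Applied to bas_nyha and fu6_nyha, this gives two separate tables. Neither is a mean and neither is a change.

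**Step 2: who is in each table.** The protocol's planned device mix for group A (sections 8.1 and 8.8.1) is 26 single-chamber + 26 dual-chamber + 53 CRT-D = 105, which reproduces the stated total.
- CRT-D share: w = 53/105 = 50.5%.
- Others: 1 − w = 52/105 = 49.5%.

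If baseline NYHA is recorded for everyone, about half of the baseline table consists of patients who by design have no 6-month value.

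**Step 3: effect of the mismatch.** Let C and N be the mean baseline NYHA of CRT-D and other patients (I–IV scored 1–4), and M the CRT-D mean at 6 months.
- Pooled baseline = wC + (1 − w)N
- Apparent change = M − pooled baseline = (M − C) + (1 − w)(C − N)

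The first term is the true CRT-D change. The second is the shift caused by the different denominators.

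The documents give no NYHA means, so C − N is an **assumption**, shown over a range. The calculation also assumes the planned mix and complete NYHA data.

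| Assumed C − N | Shift = (52/105) × (C − N) | Apparent change if true change is 0 | Apparent change if true change is −0.5 |
|---|---|---|---|
| 0.25 | +0.12 | +0.12 | −0.38 |
| 0.50 | +0.25 | +0.25 | −0.25 |
| 0.75 | +0.37 | +0.37 | −0.13 |
| 1.00 | +0.50 | +0.50 | −0.01 (−0.005 unrounded) |

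At the upper end, a true improvement of half a class would almost disappear.

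**Step 4: the alternative reading of protocol 9.2.** If baseline NYHA is recorded for CRT-D patients only, the device-mix shift is zero. The two tables can still cover different patients, because baseline NYHA is collected if available, some patients leave before 6 months, and SAP 5.4 imputes nothing. The mean change is still not specified.

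**Step 5: after pairing.** Restricting to CRT-D patients with both values puts the same patients at both visits (at most the planned 53), and the shift term is zero. No sample size, power or significance level changes.

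**The case against.** The strongest defence is that this is a silence and not a prohibition. Footnote 9 is attached to baseline NYHA (and repeated for the Plexa baseline table); fu6_nyha carries no such note. The protocol already fixes the population, time points and statistic, and the SAP merges data by patient, so a programmer could compute the change. The SAP plans no comparison of the two tables, and protocol 11.8 requires departures from the statistical plan to be documented. All of this stands, and it keeps the point small. It does not supply the missing analysis: the SAP presents itself as covering everything mandatory, and following it as written does not give the promised result.

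Some stronger readings are tempting but not supported:
- A reader might infer that footnote 9 forbids a change analysis. It rules out ordinal conversion at baseline and says nothing about change.
- A reader might infer that nominal coding is the root cause. Relabelling NYHA as ordinal would give quartiles and a median under SAP 5.1, still not a mean change. The decisive gap is the missing paired variable.
- A reader might infer that SAP 5.1 contradicts footnote 9, because a sample table there treats NYHA as ordinal. Another sample table in the same section treats it as nominal; both are dummy illustrations.
- A reader might infer that all clinical information on MultiPole Pacing is lost. Physician-rated responder status and phrenic nerve stimulation are in the SAP, and protocol 8.4.1 plans a listing of related SADEs.

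**Conclusion.** The point holds as a conflict between protocol and SAP on one descriptive result. The protocol commits to the mean NYHA change in CRT-D patients; the SAP neither defines it nor provides tables from which it can validly be read.

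The firm part is the omission and the unequal denominators, which follow from the documents. The size is conditional: a shift of about +0.12 to +0.50 class if CRT-D patients start 0.25 to 1.0 class higher than the others, on the planned 53 of 105 and with baseline NYHA recorded in all patients. It would be smaller if fewer ICD patients have a baseline value, and the device-mix part would be zero if none do.

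Severity is low. No hypothesis rests on this item, and the primary and secondary endpoints are untouched. A reader might also infer that a correct NYHA change would show what MultiPole Pacing achieves. It would not: the study is single-arm and the feature is mandatory in group A CRT-D patients, so the change cannot isolate its effect.

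**What to change.** In SAP chapter 14, add a derived variable, for example nyha_change_SAR = fu6_nyha − bas_nyha with classes I–IV coded 1–4, for CRT-D patients in the Ilivia analysis set who have both values. Report:
- the mean change;
- a baseline-by-6-month shift table, with counts improved, unchanged and worsened;
- the number of CRT-D patients missing either value.

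Amend footnote 9 to allow this coding. Reconcile protocol section 9.2 with section 8.4.1 and Table 7 on whether baseline NYHA is collected from all patients or from CRT-D patients only.

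If the sponsor prefers not to report the change, record the omission as a deviation under protocol 11.8.

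The cost is one derived variable, one table and a footnote edit, all from data already collected.
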